### **Study Design**

The study will involve 25 participants with cough hypersensitivity and 25 age and sex matched healthy controls. All participants will provide written informed consent to participate in the study, which will be approved by the Melbourne Health Human Research Ethics Committee (Australia). Before inclusion, all participants undergo screening interviews to ascertain their eligibility for the study. All participants will be non-smokers with no history of neurological disease or any recent history (over 8 weeks) of acute respiratory infections. Cough hypersensitive participants will be recruited from respiratory specialist clinics and included if they have experienced chronic cough (coughing for over 8 weeks) and are considered idiopathic/ refractory coughers (to avoid the confounds of heterogeneity of precipitating diseases). Healthy control participants will have no history of chronic respiratory disease and will be individually age and sex matched to each cough hypersensitive participant.

Participants will attend two experimental sessions. The first is used to ascertain their individual sensitivities and tolerances to inhaled challenges with capsaicin and ATP

(psychophysical testing session) and the second to determine their brain responses to challenge stimuli (brain imaging session). This is not an interventional study but rather a comparison between responses in healthy control participants versus patients with chronic cough syndrome.

All participants will first undergo a psychophysical testing session where their level of sensitivity to capsaicin and ATP is measured using a method of limits approach. The following measures of sensitivity are determined: stimulus dose evoking 2 coughs (C2), the stimulus dose required for the initial detection of an urge to cough (Cu) and the maximal suppressive stimulus dose where a participant can resist coughing (Smax). Patients will provide subjective measures of their urge-to-cough using an eleven point numerical rating scale (0, no urge-to-cough; 10, maximum urge-to-cough) evoked by single breath challenges with tussive stimuli. The capsaicin and ATP solutions are nebulized to participants via a

facemask fabricated to deliver stimuli through oral breathing (and to be compatible for hands free use in an MRI scanner). Doubling doses of stimuli are used throughout the study ranging from 0.06 $\mu$ M to 125 $\mu$ M for capsaicin and 0.45 – 232.5mM for ATP. Once the C2 dose is identified, participants will receive randomized challenges with doses two increments above and below the C2 (C2-2, C2-1, C2, C2+1 and C2+2) to accurately measure the stimulus response function for each individual. Finally, in preparation for fMRI scanning, participants will be challenged for 24 seconds with stimuli above and below the C2 dose to determine challenge stimuli doses that are tolerable for brain imaging (defined as the Smax). This session is used to ascertain each participant's sensitivities and tolerances to inhaled stimuli and to inform the participants about the design of the subsequent fMRI session.

In the second session, participants return for fMRI scanning. Structural and functional MRI data are collected on a Siemens Magnetom Trio 3 Tesla scanner (Siemens AG, Erlangen, Germany) with a 32-channel head coil located at the Monash Biomedical Imaging Facility, Melbourne, Australia. Anatomical T1 - weighted images are acquired in the sagittal plane (192 slices, 0.90 mm slice thickness, 0.84  $\times$  0.84 mm^2 in - plane resolution, echo time (TE) = 2.59 ms, repetition time (TR) = 1900 ms, flip angle = 9). Two functional MRI (fMRI) scans of 491.4 seconds duration are performed using the BOLD contrast. Functional runs are collected using a partial field of view (FOV) with a gradient-echo echo-planar parallel imaging sequence (GRAPPA, PAT factor=3, reference lines=36, TR=1790ms, TE=30ms, 27 slices, 2.5mm thickness, 1.88mm in-plane resolution, flip angle=70 degrees). This facilitates a restricted focus on the brainstem necessary to define regional activations in this area (see Figure 2).

During image acquisition, participants lay comfortably on the scanner bed with their head stabilised with foam padding and hearing protection. Participants are fitted with the facemask and apparatus used in the psychophysical testing session. Online respiratory monitors are fitted around their chest throughout the experiment (AD Instruments). A periscope mirror attached to the scanner head coil enables participants to view a projector

screen upon which visual instructional cues are presented throughout the experimental session. Within each functional scanning run, three stimulus blocks of capsaicin, three of ATP and two of saline are administered in a pseudorandom order. Each stimulus block lasts 24 seconds in duration, and is separated from the next by 36.8 seconds. Visual cues are used to time the participant's inhalation with the onset of stimulus delivery in order to standardise the respiratory cycle between participants. At the end of each challenge block, participants give a numerical rating of their urge-to-cough.

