### *Statistical Methods*

Statistical analysis of psychophysical parameters will be performed with SPSS 22.0. Independent t- tests will be used to test the effects of group on C2, Cu and Smax thresholds. A repeated-measures ANOVA is used to test the effects of group, dose and their interaction on urge-to-cough ratings in response to random stimulus challenges. Independent t-tests will be used to assess group effects on capsaicin/ ATP doses and urge-to-cough ratings associated with the fMRI scanning.

fMRI image analysis will be performed with FEAT, version 5.98. Regressors for each dose of capsaicin/ ATP and rating events will be included in a general linear model that also includes motion parameters and confound variables to take account of physiological noise. Contrasts for capsaicin/ ATP doses will be averaged across the three scans for each participant and used in the analysis of group and between-group effects. Group contrasts include high doses for all participants (Like-Behaviour), and activation levels will be tested for correlations with Cu and frequency of coughing during repeated stimulus challenges. Higher level analyses will be carried out for inter-group averaging and between-group comparisons. Z (Gaussianised T/F) statistic images are thresholded to define clusters of contiguous voxels activated at a significance level of  $Z > 2.3$ . To correct for multiple comparisons, a corrected cluster probability threshold (based on Gaussian Random Field Theory of  $p < 0.05$ ) is applied. Between-group contrasts are made using two different comparisons: i) during the inhalation of Smax for all individuals in both groups (matched urge-to-cough sensation). Activation levels associated with Smax doses are tested for relationships with the Cu threshold and the frequency of coughing during the psychophysical sessions.

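### Session 1 describes no blank inhalation, so a lower Cu in patients cannot be told apart from readier reporting or a response to the aerosol itself

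*Combined protocol and SAP*

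**What the plan says.** Study Design lists three thresholds from the psychophysical session: C2, Cu and Smax. Cu is "the stimulus dose required for the initial detection of an urge to cough (Cu"), and sensitivity to both agents is "measured using a method of limits approach". Urge is scored from 0 (none) to 10, and the ratings are those "evoked by single breath challenges with tussive stimuli".

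The dose ladder begins at an active concentration: "Doubling doses of stimuli are used throughout the study ranging from 0.06" µM for capsaicin, with 0.45 mM the lowest ATP dose. Once C2 is known, "participants will receive randomized challenges with doses two increments above and below the C2". All five of these doses are active. No saline, catch trial or masking of content is described for this session.

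Saline enters only at imaging, where in each run "three stimulus blocks of capsaicin, three of ATP and two of saline are administered in a pseudorandom order". Ratings are taken there too: "At the end of each challenge block, participants give a numerical rating of their urge-to-cough".

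Under Statistical Methods, "Independent t- tests will be used to test the effects of group on C2, Cu and Smax thresholds". Cu is also related to activation at Smax. No analysis refers to the saline ratings.

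**The concern.** A first-urge threshold depends on what the participant feels and on how readily the participant calls it an urge. Without blanks in the series, the data hold no estimate of the second part.

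The two groups could differ on that second part for reasons unrelated to ATP or capsaicin. Patients are recruited from respiratory specialist clinics and presumably know their status. The background section also names aerosol sprays among the everyday triggers that patients report, so a nebulised mist through a facemask might produce an urge in them whatever it contains. Either route lowers Cu in patients with no change in sensitivity to the agent.

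This matters because the hypothesis is specific to ATP. A lower Cu for ATP would naturally be read as sensitisation of an ATP-responsive pathway, and the planned test cannot exclude the non-specific explanation.

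**Working it through.** The plan gives no expected value, SD, false-report rate or power for Cu, so there is no figure of its own to reproduce; its power statement concerns BOLD signal only. What follows is an illustration under assumptions.

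**From the plan**
- 25 patients and 25 controls, compared by independent t-test.
- Doubling doses. Capsaicin: log2(125/0.06) = 11.0 doublings, about 12 levels. ATP: log2(232.5/0.45) = 9.0 doublings, about 10 levels.

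**Assumed**
- Ascending order and a two-sided 5% test.
- True threshold at mean step 6, between-person SD 1.5 steps, identical in both groups.
- A chance f of reporting an urge at each inhalation below threshold, independent from step to step.

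**Closed form, Cu scored at the first report.** For a true threshold at step T:
- P(Cu recorded too early) = 1 − (1 − f)^(T−1)
- Mean recorded step = [1 − (1 − f)^T] / f

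With T = 6:
- f = 0.05: 1 − 0.95^5 = 23%; mean step 5.30, a shift of 0.70
- f = 0.10: 1 − 0.90^5 = 41%; mean step 4.69, a shift of 1.31
- f = 0.20: 1 − 0.80^5 = 67%; mean step 3.69, a shift of 2.31

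Against controls at 5%, patients at 10% would show a Cu lower by 1.31 − 0.70 = 0.61 doublings, and patients at 20% one lower by 2.31 − 0.70 = 1.61.

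**Simulated rate of a false group difference, 12 steps, controls at f = 0.05.** Ranges cover repeat runs.

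| Scoring rule for Cu | Patients 10% | 15% | 20% |
|---|---|---|---|
| First report | 19–20% | 51–54% | 80–81% |
| First of two consecutive reports | 6–7% | 9–11% | 20–21% |
| First report sustained thereafter | 5–6% | 6–7% | 7% |

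With f = 0.05 in both groups the rate is 4–5% under the first-report rule, as it should be. The simulated shifts under that rule (about 0.6, 1.2 and 1.7 doublings) agree with the closed form.

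**Other settings, first-report rule, patients at 10/15/20%**
- SD 2.5 steps: about 16%, 41% and 69%.
- 10-step ladder with threshold at step 5: about 16%, 40% and 66%.
- Threshold near step 3: about 8%, 15% and 26%.

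**A persistent shift instead of isolated false reports.** In a signal-detection version (12 steps, within-person noise SD 1 step, first report, between-person SD 1.5 to 2.5), a patient criterion lower by one step moves mean Cu by about one step and gives 25–51% false differences. Two steps give 75–98%. A stricter scoring rule would not remove a shift of this kind, because the reports continue at every higher dose.

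**The case against.** Several points on the other side are sound.

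- **Silence is not absence.** The documents do not say that blanks are left out or what participants are told about each inhalation, and the analysis plan points to previously published methods that cannot be checked here. A reader might infer that every session 1 inhalation is known to be active; the text does not establish that. The defensible wording is that no blank is described.
- **One early report need not settle Cu.** The same session must go on to find C2, and urge is graded from 0 to 10, so an isolated early rating followed by zeros could be seen and discounted. Dose order, number of series and scoring rule are not stated. The highest error rates therefore describe one possible rule, not the protocol's rule.
- **The activation–Cu correlation.** A reader might conclude that it would be spurious as well. That was not computed. False reports unrelated to BOLD signal add noise and would tend to weaken a correlation. Creating one would require reporting tendency to be tied to activation, or pooling of groups that differ in activation.
- **Scope.** Cu is one of three thresholds, and the primary comparison concerns BOLD signal and associated psychometrics. C2 depends on counted coughs.
- **Saline correction can remove real disease.** The protocol frames chronic cough as hypersensitivity with altered central processing, so an urge to a bland inhalation may belong to the phenotype. Subtracting it in the main analysis could remove a true difference.

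These limit the size and reach of the point and shape the remedy. They do not answer the core of it. The randomised challenges around C2 are all active, so nothing described in session 1 can show how often either group reports an urge to an inert inhalation.

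**Conclusion.** The point stands as one of interpretation. On the plan as written, a group difference in Cu cannot be attributed to sensitivity to ATP or capsaicin, because readiness to report and a non-specific aerosol response would look the same.

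The size of any bias is unknown. The range of about 20–80% false differences rests on assumed false-report rates of 10–20% against 5%, an ascending series and a first-report rule. It falls close to the nominal 5% if isolated false reports are screened out by a sustained-report rule, but not if patients hold a persistently lower criterion. The documents contain no data showing that patients report more readily, and this review does not claim that they do.

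The consequence is confined to the Cu comparison and, more loosely, to urge ratings that are not referred to saline. It is worth correcting because the remedy is cheap and the hypothesis is stimulus-specific.

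**What to change.** 1. **Study Design, psychophysical session.** Intersperse a few saline inhalations at unannounced positions in each dose series, through the same mask, and report the rate and rating of urge to saline by group. This uses equipment already in place; the downside is a slightly longer session. State the Cu scoring rule in the same paragraph. If blanks are already routine, saying so is enough.

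2. **Statistical Methods.** Compare the scanner saline-block urge ratings between groups. Add two sensitivity analyses: scanner urge ratings as stimulus minus saline, and the group comparison of Cu adjusted for saline rating. Keep the unadjusted analyses as planned, since the saline response may be part of the disease. The block ratings should already be collected, so this costs wording only. Two saline blocks per run over the two runs in Study Design give four per person; Statistical Methods speaks of three scans, so the count should be reconciled. These ratings come from another session with 24-second blocks, so they are a partial check and do not replace item 1.

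3. **Interpretation.** State in advance that a lower Cu in patients will be called stimulus-specific only if it persists in these checks.

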### **PRELIMINARY DATA**

#### *Peripheral effects of ATP via P2X3 receptors*

ATP has been shown to be a tussive agent particularly on chronic cough patients who were more sensitive than non-cough subjects to inhaled ATP (27). ATP has been shown to augment the cough response to capsaicin in patients with asthma (28). Gefapixant at a single oral dose of 50 mg did not modulate capsaicin cough responses in normal volunteers and chronic cough subjects while inhibiting ATP-induced cough particularly in chronic cough

subjects (22). These observations would suggest that ATP has a direct effect on the sensory neurons that evoke coughing through the activation of P2X3 receptors (detailed above).

*The use of fMRI to provide insights into the peripheral and central sites of activation by ATP/P2X3 activation*

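### A C2 within the top or bottom two dose steps leaves an incomplete C2±2 set, and the planned repeated-measures ANOVA would usually drop that participant's valid urge-to-cough ratings for that agent

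*Combined protocol and SAP*

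**What the plan says.** Study Design sets the dose ladder: "Doubling doses of stimuli are used throughout the study ranging from 0.06" µM up to 125 µM for capsaicin, and 0.45 to 232.5 mM for ATP. Once C2 (the dose evoking two coughs) is found, "participants will receive randomized challenges with doses two increments above and below the C2 (C2-2, C2-1, C2, C2+1 and C2+2"). Nothing in that section confines C2 to the interior of the ladder or says what happens when a step falls outside it.

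Statistical Methods states: "A repeated-measures ANOVA is used to test the effects of group, dose and their interaction on urge-to-cough ratings", and identifies these as "urge-to-cough ratings in response to random stimulus challenges". On software it says: "Statistical analysis of psychophysical parameters will be performed with SPSS 22.0". It gives no rule for missing dose levels and names no mixed model. Separately, independent t-tests "will be used to test the effects of group on C2, Cu and Smax thresholds".

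**The concern.** Two steps are needed on each side of C2, but the ladder is finite. A participant whose C2 falls on one of the two lowest or two highest steps cannot receive all five doses within the stated range. A classical repeated-measures ANOVA needs every within-participant level, and its usual implementation deletes a case with any level missing. Three or four ratings that were properly collected would then go unused.

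The situation is foreseeable for ATP at the top of the range. The preliminary data section reports that "ATP has been shown to be a tussive agent particularly on chronic cough patients who were more sensitive than non-cough subjects to inhaled ATP", and the protocol describes ATP as a relatively weak cough stimulus in healthy people. High ATP C2 values are therefore plausible in controls, and the loss may be unequal between groups. At stake is the precision of the group and group-by-dose tests on urge-to-cough ratings, with only 25 participants per group.

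**Working it through.** **Steps in each ladder** (ranges from Study Design). Number of steps = log2(max/min) + 1.
- Capsaicin: log2(125/0.06) = 11.02, so 12 steps.
- ATP: log2(232.5/0.45) = 9.01, so 10 steps.

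**Where the full set fits.** Two steps are lost at each end.
- Capsaicin: 12 − 4 = 8 positions, from 125/2⁹ = 0.24 µM to 125/2² = 31.25 µM.
- ATP: 10 − 4 = 6 positions, from 232.5/2⁷ = 1.8 mM to 232.5/2² = 58.1 mM.
- With C2 one step from an end (for example 116.25 mM ATP), four levels are available. With C2 at an end (232.5 mM), three are.

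**Meaning of dose in the ANOVA.** If dose meant absolute concentration, no participant would have more than 5 of the 12 or 10 levels. The factor must therefore be the step relative to C2. A standard repeated-measures ANOVA routine, tried with one cell removed, refused to run. The usual SPSS repeated-measures procedure deletes the whole case.

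**Illustrative cost for ATP.** The documents give no C2 distribution, so these inputs are assumed:
- 25 per group (from the protocol) and a log-normal cough threshold;
- C2 is the first ladder dose at or above the threshold;
- control median 14.5, 29 or 58 mM, with the patient median a quarter of it;
- SD 1.0, 1.5 or 2.0 doublings.

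Example with control median 29 mM and SD 1.5 (Φ is the standard normal distribution function):
- Controls reaching C2: 25 × Φ(3/1.5) = 24.43. Controls with the full set: 25 × [Φ(1/1.5) − Φ(−5/1.5)] = 18.68.
- Patients reaching C2: 25 × Φ(5/1.5) = 24.99. Patients with the full set: 25 × [Φ(3/1.5) − Φ(−3/1.5)] = 23.86.
- Approximate standard-error ratio, complete cases against everyone with a C2: √[(1/18.68 + 1/23.86)/(1/24.43 + 1/24.99)] = √(0.09544/0.08095) = 1.09.

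The same formula in all nine scenarios gives:

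| SD (doublings) | control median 14.5 mM | 29 mM | 58 mM |
|---|---|---|---|
| 1.0 | 1.01 | 1.05 | 1.22 |
| 1.5 | 1.05 | 1.09 | 1.21 |
| 2.0 | 1.10 | 1.12 | 1.21 |

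A simulation of the ratings (6000 runs per scenario) compared complete cases with a random-intercept mixed model. It agreed, with increases of 1% to 11% at the two lower medians and 21% to 23% at 58 mM. It did not fit random slopes.

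**Participants with no C2.** In the same scenarios the expected number of controls whose threshold exceeds 232.5 mM runs from about 0 to 4 of 25. The largest value is at a 58 mM median and SD 2.0: 25 − 25 × Φ(2/2.0) = 4.0.

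**The case against.** The strongest reply is that the documents establish only which ladder positions are incompatible with the full set, not that any participant will occupy them. That stands. A reader might infer that a third of participants (4 of 12) would be lost for capsaicin, or 40% (4 of 10) for ATP. Positions are not participants, and the documents do not support that inference.

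The illustration also leans towards the top of the ladder. The geometric midpoint of the ATP range is √(0.45 × 232.5) = 10.2 mM, and all three assumed control medians exceed it. The 58 mM median is the last position where a full set fits, so about half the controls are truncated by construction. The preliminary data support a direction but no median, spread or fourfold gap.

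Complete-case deletion is the usual behaviour of the named method, not a decision written in the plan. The SAP refers to the team's published methods, which may handle truncated sets. This stands as a limit on certainty, but the plan as written offers no other handling.

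Three further readings go too far:
- **Bias.** Loss that depends on sensitivity might suggest bias, but the documents do not say how ratings relate to C2 at a given step. Nor can the simulation reassure, because it assumed no such relation.
- **Imaging.** The fMRI contrasts are made at Smax and do not use the C2±2 levels. Nor does the point extend to the correlations with cough frequency. The SAP also words that measure as "the frequency of coughing during the psychophysical sessions", which does not settle which challenges supply it.
- **Doses beyond the range.** The range is stated to hold throughout the study, so truncation is the natural reading, and no safety concern follows.

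**Conclusion.** The point holds as a minor one. It is certain from the stated ranges that 4 of 12 capsaicin and 4 of 10 ATP positions for C2 cannot hold the five-dose set. Given complete-case handling and a separate analysis for each agent, a participant at one of those positions is lost from that agent's urge-to-cough ANOVA despite having three or four valid ratings.

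The frequency is unknown and may be near zero. If the assumed ATP scenarios are near the truth, the standard error of the group effect grows by about 1% to 12% for control medians of 14.5 to 29 mM. The increase of 21% to 22% needs a control median at 58 mM. No claim is made about bias in either direction.

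The t-tests on Cu and Smax and the fMRI contrasts at Smax are not affected by the missing levels. The C2 t-test is not affected by them either, but anyone who never reaches C2 has no value to enter in it. That is a separate consequence of the same dose ceiling.

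**What to change.** 1. In Study Design, state that the C2±2 challenges are truncated at the minimum and maximum of each range. This makes explicit what the fixed range already implies. For capsaicin it agrees with the 0.0038% given under Risks: 125 µM × 305.4 g/mol (assumed molar mass) = 38.2 mg/L = 0.0038% w/v.
2. In Statistical Methods, replace the repeated-measures ANOVA of the ratings with a linear mixed model for each agent, using every challenge given. Include group, categorical C2-relative step and their interaction, with Satterthwaite degrees of freedom. Use a participant random intercept plus a random step slope, or an unstructured covariance, because a random intercept alone is too restrictive when individual response slopes differ.
3. Report, by group and agent, the number of truncated sets and the number of participants who never reach C2.

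The cost is one sentence in the protocol, revised SAP wording and minor analysis work, with no extra participants, visits or doses. If truncation never occurs, essentially nothing is lost. The model assumes that ratings at steps not given would follow the same pattern, given group and step, as those observed. It cannot recover those ratings, and it does not help participants without a C2.
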